### 13. Community-Based Participatory Research

All involvement of community advisory board for research will be conducted inside MSSM.

### 14. Sharing of individual and study Results with Subjects:

Results will not be communicated with study participants as part of the study is not to influence decision making.

### 15. External IRB Review History

N/A

### 16. Control of Drugs, Biologics, or Devices:

N/A

Comprehensive Home-based Self-management Support for COPD Patients
PI: [name] [name]
NCT04533412
Document Date: 9-06-2021

STATISTICAL ANALYSIS PLAN

We compared the baseline characteristics of study participants in the intervention and control groups using a t-test, Wilcoxon Rank Sum test or chi-square test, as appropriate. We used a difference-in-differences (DiD) approach to examine the effects of intervention and control over time. Analyses were performed using generalized linear models with a REPEATED statement (SAS Proc GENMOD). As a feasibility trial, the study was not powered to detect statistically significant differences for outcomes between intervention and control arms, though $P < 0.05$ was considered statistically significant for all outcomes analyses. All analyses were performed using SAS software, version 9.4 (SAS Institute, Inc., Cary, NC).

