A.4) The Screener is the tool CHWs will use to comprehensively and efficiently identify barriers to COPD self-management and disease control. Most items on the current SAMBA screener are applicable to chronic illness self-management and include costs of medications and medical care, mental health disorders like anxiety and depression, alcohol and other substance use disorders, tobacco use, physical and cognitive impairment, social support, and environmental factors (e.g., stable housing, exposure to second hand tobacco smoke). Inhaler technique, controller medication adherence, and action plans are also relevant to COPD patients. Unique COPD items will include behaviors pertaining to oxygen use and exercise, acceptance of influenza and pneumococcal pneumonia vaccines, and beliefs about COPD illness and medications. The screener is implemented after the RA enrolls a participant in the study. The screener is only used for participants in the intervention group.

B. Phase II will focus on intervention implementation and evaluation (months 13-36). We will randomize 58 COPD patients (29 per arm) to the SaMBA-COPD intervention or an attention control and follow them for 9 months to assess health and self-management behavior (SMB) outcomes.

B.1) CHW Training. Training will cover the basics of COPD pathophysiology and treatments and COPD SMB. It will also review the procedures of the SaMBA-COPD model and core skills, including motivational interviewing, communication with healthcare providers, and other topics. After training, CHWs will engage in observed role play until they have mastered the basic

	Protocol Name:	Comprehensive Home-based Self-management Support for COPD Patients
	Principal Investigator:	[name], MPH
	Primary Contact Name/Contact Info:	[name]; [contact]; [contact]
	Date Revised:	4/16/21
	Study Number:	STUDY-18-01345

elements of the protocol. They will then work with actual patients during pre-testing. CHWs will be observed in the field and must be certified before they can provide support to patients independently as was required for SAMBA. Supervisors will do monthly field observations to ensure that quality is maintained.

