Research Recruitment and Study Arm Assignment: We will identify potentially eligible patients and will obtain permission from the physician to recruit their patient. We will send a letter to the patient describing the study. One week later, the RA will phone the patient to answer questions and check eligibility of the participant. Eligible patients will be scheduled for an in-person or phone baseline interview, consented and enrolled in the study. We will assess the participant's inhaler technique, electronic medication adherence, and physical activity through a wearable activity monitor. The data from the electronic medication adherence device is for research purposes only. There are no studies demonstrating that providing such data to patients or their doctors improves their medication adherence, thus providing these data to them is unwarranted. The participant will then be randomized to the intervention or control arm.

B.3) SaMBA-COPD Intervention.

	Protocol Name:	Comprehensive Home-based Self-management Support for COPD Patients
	Principal Investigator:	[name], MPH
	Primary Contact Name/Contact Info:	[name]; [contact]; [contact]
	Date Revised:	4/16/21
	Study Number:	STUDY-18-01345

Step 1: Outreach and Engagement. The project manager will notify the CHW supervisor when an eligible and consented patient is randomized to receive care the intervention and will provide the patient's name and contact information (see Description of Procedures Being Performed for recruitment and randomization). The CHW will call the patient within 7 days of consent to schedule a home visit. The CHW will encourage caregivers to join all meetings.

Step 2: Intake. The CHW will perform an intake interview that includes collection of basic information about the patient and their health and healthcare, including medications, intended to enable them to understand their health problems and provide them with chronic illness self-management support.

Step 3: Symptom assessment, medication adherence, and inhaler technique. The CHW will assess the patients' symptoms, adherence to medications, and check inhaler technique following a standardized protocol, and correct errors in inhaler use if identified.

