- Rather than bringing the Principal Investigator or other licensed clinician into the room to meet with the participant in person, the clinician will be contacted via phone and, with the participant's permission, will be given access to join the video conference and conduct an additional assessment via this platform.
- If the clinician determines that that participant is at elevated risk for suicide, the patient is notified by the clinician that 911 will be called and that this will result in an ambulance being sent to their residence to make sure that the subject is okay. The study coordinator remains on the telephone with the patient until the ambulance arrives. The 911 operator is notified if the patient ends the video conferencing call abruptly or hangs up.

	Protocol Name:	Comprehensive Home-based Self-management Support for COPD Patients
	Principal Investigator:	[name], MPH
	Primary Contact Name/Contact Info:	[name]; [contact]; [contact]
	Date Revised:	4/16/21
	Study Number:	STUDY-18-01345

e. Randomization. Randomization will occur immediately after the baseline interview is complete. To obtain the assignment, the RA will access an online program in REDCap that implements the algorithm.

f. Control Arm. The attention control is designed to isolate the impact of screening for self-management barriers, targeted self-management support, and HBEP. The attention control will consist of 3 visits by a CHW to the home to review the COPD education booklet (COPD 1-2-3). During the first visit, this CHW will review the COPD 1-2-3 booklet in its entirety with the patient. During visits 2 and 3, the CHW will make a visit to "check in" with the patient, ask how they are doing with their respiratory symptoms, and review any sections of the COPD 1-2-3 booklet the patient chooses. The CHW will recommend visits every 2 months but the patient and CHW may choose to modify the interval as needed. If the patient appears to be experiencing worsening respiratory symptoms during any visit, the CHW will notify the patient's physician.

g. Quantitative Data Collection. Baseline, 6- and 9-month interviews will be in-person or over the phone in English or Spanish. Bilingual RAs will conduct them at home or in clinical spaces, by patient preference, using laptop computers and REDCap software, as we do with all of our research.

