Primary Outcomes: COPD symptoms, inhaler technique, and exercise activity. COPD symptoms will be measured with the 8-item COPD Assessment Test (CAT) (score range 0-40), the 14-item Chronic Respiratory disease Questionnaire (CRQ), and the Medical Research Council Scale. Inhaler technique: We will assess proficiency in use of MDI and DPI placebo devices (Spirit Medical Devices, Murrysville, PA) and medication tracking devices (Propeller Health, Madison Wisconsin) using validated checklists and adapt these checklists for technique assessment with users of Elipta and Respimat inhalers. The Propeller Health devices can aid patients in medication adherence and understanding of their triggers for COPD and asthma. Exercise in the past 7 days will be measured with the 13-item Physical Activity Adult Questionnaire (PAAQ) and a wearable activity monitor, the Actigraph, which will be worn for 1 week intervals at baseline, 6 and 9 months. Secondary Outcomes. Self-reported medication adherence will be measured with the self-reported Medication Adherence Reporting Scale (MARS)., and with an electronic monitoring device that is attached to the inhaler. Exercise tolerance will be measured at baseline, 6- and 9-months using the 6- minute walk test (6MWT). We will ask about use of an action plan for COPD exacerbation.

h. Fidelity. Fidelity will be assessed through abstraction of CHWs' documentation in Community Health Works' documentation, direct observation of the CHWs, and qualitative exit interviews with patients and CHWs. The project manager will conduct unannounced

	Protocol Name:	Comprehensive Home-based Self-management Support for COPD Patients
	Principal Investigator:	[name], MPH
	Primary Contact Name/Contact Info:	[name]; [contact]; [contact]
	Date Revised:	4/16/21
	Study Number:	STUDY-18-01345

observations of each CHW monthly during the trial. She will also audio/video tape these encounters to review with the CHW for skills development.

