i. **Qualitative Data Collection and Analysis.** We will conduct semi-structured exit interviews with patients and CHWs to assess feasibility and perceptions of SaMBA-COPD to guide refinement. Interviews will follow the month 9 interview or at study dropout (30-45 minutes; compensation, \$20). Topics will include satisfaction, burden (physical, emotional, social), convenience, perceived positive or negative effects, and appropriateness. At trial completion, we will conduct qualitative interviews with CHWs and their supervisor and PR staff and physicians to assess the same topics. All interviews will be audio/video-recorded. These interviews will be used for internal evaluation and quality improvement.

j **Quantitative Data Analysis.**

Primary analyses. We will analyze outcomes on the intention-to-treat principle. The primary outcomes are CAT score, ICS technique, and PAAQ scores at 9 months.

Description of Data that Will Be Collected Including Long-Term Follow-Up

Disease beliefs: will be measured with the brief Illness Perceptions Questionnaire (IPQ; available in English and Spanish) that includes items for each of the 5 cognitive domains of the SRM.(15) Medications Beliefs: We will use the Beliefs about Medicines Questionnaire, an English and Spanish validated 10-item scale that measures beliefs about controller medication in 2 subdomains: necessity and concerns (reliability: 0.80). (16) Items will be added to assess expectations of benefits and emotional representations about medications (worried about side effects or addiction, upset about medication regimen, etc.).

Adherence: COPD controller medication adherence, electronically measured: Objective measurement using the Smartinhaler electronic device for metered dose inhalers (MDIs) and the Smartdisk for dry powder inhalers (DPIs) for 4 weeks after each research interview. RAs will attach the monitoring device to the inhaler, and patients will return them in a pre-stamped envelope. Adherence will be defined as use of medications on #70% of days prescribed, a commonly applied convention.

Cognitive: Quick mild cognitive impairment screen (QMCI).

Lifestyle: physical activity, electronically measured: objective measurement using Actigraph. Physical activity adult questionnaire (PAAQ). Smoking/alcohol/drug activity. Activities of daily living questionnaire (ADL), general health (single item). Comorbidities (Charlson Index).

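### Difference-in-differences is usually less precise than baseline adjustment when patients are randomised after baseline; add a baseline-adjusted 9-month estimate with a 95% CI for the continuous primary outcomes

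*SAP*

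**What the plan says.** The SAP names one approach to treatment effects: "We used a difference-in-differences (DiD) approach to examine the effects of intervention and control over time". The tool is GENMOD: "Analyses were performed using generalized linear models with a REPEATED statement (SAS Proc GENMOD". It lists no model terms, working correlation or contrast, and its only stated criterion is P < 0.05. It also says the trial was not powered for between-arm differences in outcomes.

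Protocol section 3(e), B. Phase II, sets the size: "We will randomize 58 COPD patients (29 per arm". Item e (Randomization) sets the timing: "Randomization will occur immediately after the baseline interview is complete". The paragraph on recruitment and study arm assignment agrees; after describing the baseline assessments it says "The participant will then be randomized to the intervention or control arm".

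Item g gives the schedule: "Baseline, 6- and 9-month interviews will be in-person or over the phone in English or Spanish". Item j fixes the endpoint: "The primary outcomes are CAT score, ICS technique, and PAAQ scores at 9 months".

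Neither document mentions adjustment for baseline, an estimated 9-month difference between arms, or a confidence interval.

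**The concern.** Because allocation follows the baseline measurement, any baseline difference between the arms is chance. DiD and baseline adjustment therefore target the same quantity, the 9-month difference between arms, and both are unbiased with complete data. They differ in how they treat the chance imbalance. DiD subtracts all of it, which fixes the baseline coefficient at 1. Adjustment subtracts the share that the data support. When the true slope of the 9-month value on baseline is below 1, DiD over-corrects and adds noise.

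A feasibility trial that disclaims power is useful mainly for its estimates and intervals, which feed the design of the next study. Wider intervals than the same 58 patients could give are an avoidable loss.

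**Working it through.** **Inputs from the documents:** 58 patients, 29 per arm; individual randomisation after baseline; measurements at baseline, 6 and 9 months; DiD by GENMOD with REPEATED. 2 × 29 = 58 agrees, but no power calculation, SD, correlation or dropout rate is given, so no figure of the plan's own can be reproduced.

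**Assumptions:** correlation ρ between baseline and 9 months of 0.3 to 0.9; baseline SD equal to k times the 9-month SD, with k = 0.8, 1.0 or 1.2; normal outcomes; complete data; DiD in its usual form (arm, time, arm × time).

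**Step 1. Does the REPEATED statement already recover the precision?** No. A GEE with arm, visit and arm × visit was fitted to simulated complete data. Its 9-month interaction equalled the plain difference in mean changes to machine precision.

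**Step 2. Variances,** in units of the squared 9-month SD, with n per arm:

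- Var(DiD) = (2/n)(1 + k² − 2ρk)
- Var(adjusted) = (2/n)(1 − ρ²) × [1 + 1/(2n − 4)]; the bracket is the price of estimating the slope, 1 + 1/54 = 1.019 at n = 29.

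The large-sample ratio is (1 − ρ²)/(1 + k² − 2ρk). The denominator equals (1 − ρ²) + (k − ρ)², so the ratio never exceeds 1. It equals 1 only when k = ρ, that is, when the slope ρ/k is 1. With k = 1 it reduces to (1 + ρ)/2.

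**Step 3. Worked case, ρ = 0.5, k = 1.**

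- DiD: (2/29)(1 + 1 − 1) = 0.0690, SE 0.263
- Adjusted: (2/29)(0.75)(1.019) = 0.0527, SE 0.230
- t-based half-widths (56 and 55 df): 0.526 and 0.460, which is 12.6% narrower.

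**Step 4. Across the range,** simulated at 29 per arm (40,000 runs per cell), adjusted-to-DiD variance ratio:

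| ρ | k = 0.8 | k = 1.0 | k = 1.2 |
|---|---|---|---|
| 0.3 | 0.80 | 0.66 | 0.54 |
| 0.5 | 0.91 | 0.77 | 0.62 |
| 0.7 | 1.00 | 0.87 | 0.68 |
| 0.8 | 1.02 | 0.91 | 0.71 |
| 0.9 | 0.97 | 0.96 | 0.69 |

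With k = 1 and ρ of 0.3/0.5/0.7/0.8/0.9, the mean 95% half-width falls from 0.62/0.52/0.41/0.33/0.234 to 0.50/0.46/0.38/0.32/0.230 SD, which is 19/13/7/4/2% narrower. With k = 0.8 the gain is about 10% and 5% at ρ of 0.3 and 0.5, and about nil from 0.7 up. With k = 1.2 it is 27/21/17/16/17%. At an assumed 23 per arm (58 less about 20%) with k = 1, the ratios are 0.67/0.77/0.87/0.91/0.98.

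**Step 5. Two reference points, k = 1.** At ρ = 0.3, DiD is less precise than ignoring baseline altogether (SE 0.311 against √(2/29) = 0.263). At ρ = 0.5, DiD would need 29 × 2/1.5 ≈ 39 per arm to match adjustment at 29.

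**Step 6. Form of a repeated-measures version.** One common baseline slope for both visits loses precision if the correlation decays. With baseline correlations of 0.7 at 6 months and 0.3 at 9 months, and 0.5 between those visits, the variance ratio to DiD is 0.66 with visit-specific slopes and 0.72 with one common slope. With complete data, the visit-specific model gives the same 9-month estimate as single-visit ANCOVA.

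**The case against.** The main objection is that there is no error here. DiD is a valid estimator, the trial disclaims power, and the gain rests on correlations and SDs that the documents do not give. That is right, and it limits this to a suggestion.

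Four narrower points:

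- **Interval type.** The half-widths compare t-based intervals on both sides. If the reported DiD interval is an uncorrected sandwich z interval, the visible narrowing with equal SDs is only about 15/9/3/0/−2% at ρ of 0.3/0.5/0.7/0.8/0.9. That interval, however, covers about 94% rather than 95%, so t against t is the fairer comparison. The SAP does not say which is used.
- **Model terms.** The SAP lists none. A model that constrained the baseline means to be equal would already be close to baseline adjustment. DiD normally includes an arm main effect, so this is possible but is not what the name implies.
- **Scope.** Inhaler technique will be assessed "using validated checklists and adapt these checklists for technique assessment with users of Elipta and Respimat inhalers", with no scoring rule, so the figures do not cover it if it is binary. CAT has a stated 0–40 range; PAAQ scoring is not described. Item g also lists the Actigraph under primary outcomes, and its baseline wear week could run past randomisation. Item j's list of primary outcomes leaves it out, and a contaminated baseline would affect DiD too.
- **Post hoc choice.** The SAP is in the past tense and sets P < 0.05 for all outcomes. A second estimate adds analytic freedom. Labelling reduces that problem but does not remove it.

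**Conclusion.** The concern holds, as a point of precision worth considering. With individual randomisation after baseline, the large-sample variance of the adjusted 9-month difference is never larger than that of DiD for a continuous outcome, and it is smaller unless the slope on baseline is 1. At 29 per arm, over the assumed correlations and SD ratios, the 95% interval is between 0 and 27% narrower. The gain is material at low to moderate correlation and negligible near 0.9 with equal SDs. In the least favourable case, with a slope near 1, adjustment costs about 2% in variance. This rests on normal, complete data and the usual form of DiD. Conclusions drawn from DiD remain valid.

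**What to change.** For each continuous primary outcome in item j (CAT, PAAQ, and technique only if scored continuously), report a baseline-adjusted 9-month difference between arms with a 95% CI beside the DiD result. Either of two models will do; name one before fitting it:

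- a single-visit ANCOVA of the 9-month value on arm and baseline, with t-based inference; or
- a repeated-measures model of the 6- and 9-month values with arm, visit, arm × visit, baseline and baseline × visit (or a common baseline mean), unstructured covariance and Kenward-Roger degrees of freedom. This one also uses patients who have a 6-month but no 9-month value.

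Keep the DiD result, label the adjusted analysis as added later with its date, and state the terms of the DiD model. The cost is one extra post hoc model per outcome and no new data.

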**MSSM Additional Monitor (Co-I):**

Last Name: [name]  
 First Name: [name]  
 Academic Title: MA, MPH, PhD  
 Department: Division of General Internal Medicine & Geriatrics  
 Mailing Address: [REDACTED], [name]  
 [contact])  
 E-mail: [contact]

*3. Justify your choice of principal monitor in terms of the assessed risk to the research subject's health and wellbeing. In high risk studies when the principal monitor is independent of the study staff, indicate the individual's credentials, relationship to the PI, and the rationale for selection.*

The Principal Investigator is the individual who understands the benefits and risks associated with the research. The clinical experience and expertise in the field of COPD and self-management behavior interventions of the principal monitor is an adequate choice to assess the risk of research subjects' health and well-being.

*4. List the specific items that will be monitored for safety (e.g., adverse events, subject compliance with the protocol, drop outs, etc.).*

The DSMB will monitor patient safety, consider new scientific or therapeutic developments that could impact safety or trial ethics, and make recommendations to continue, terminate, or modify the trial based on interim analyses. The DSMB will specifically review: 1) hospitalization and mortality rates; 2) study disenrollment unrelated to death; 3) any patient, caregiver, and healthcare provider concerns. Adverse events that may result in subject withdrawal include disruption of previously established regular care such that the patient's health is jeopardized or excessive burden created by the time required to participate in the study.

*5. Indicate the frequency at which ACCUMULATED safety and data information (items listed in number 3 above and interim analysis of efficacy outcomes) will be reviewed by the monitor(s) or*

	Protocol Name:	Comprehensive Home-based Self-management Support for COPD Patients
	Principal Investigator:	[name], MPH
	Primary Contact Name/Contact Info:	[name]; [contact]; [contact]
	Date Revised:	4/16/21
	Study Number:	STUDY-18-01345

*the Data Monitoring Committee (DMC). Although this information must be reviewed at least annually, the higher the study risks, the more frequently reviews must be scheduled.*

Every 6 months for a total of 3 meetings

*6. Where applicable, describe rules which will guide interruption or alteration of the study design.*

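### The SAP's GENMOD difference-in-differences names no working correlation and no missing-data method; under independence, score-related dropout that differs by arm would bias the 9-month effect

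*SAP*

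**What the plan says.** The SAP is a single paragraph. On the outcome model it says "We used a difference-in-differences (DiD) approach to examine the effects of intervention and control over time" and "Analyses were performed using generalized linear models with a REPEATED statement (SAS Proc GENMOD". That is GEE. The paragraph gives no model terms, link or distribution, working correlation, visit at which the contrast is taken, missing-data method or sensitivity analysis. It says that "the study was not powered to detect statistically significant differences for outcomes between intervention and control arms", yet P < 0.05 "was considered statistically significant for all outcomes analyses".

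The protocol supplies the rest of the frame. Section 3(e), Phase II: "We will randomize 58 COPD patients (29 per arm) to the SaMBA-COPD intervention or an attention control". Item j, Quantitative Data Analysis: "We will analyze outcomes on the intention-to-treat principle", and "The primary outcomes are CAT score, ICS technique, and PAAQ scores at 9 months". Interviews take place at baseline, 6 months and 9 months. Item c, Recruitment and Interviewing, says when a patient who misses interviews counts as a dropout. Neither document gives an expected dropout rate or says how a missing 9-month value is treated.

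**The concern.** If no correlation type is named, GENMOD fits GEE under independence. With arm, visit and their interaction in the model, each fitted mean is simply the observed mean of that arm at that visit. The difference-in-differences therefore takes everyone's baseline away from the 9-month mean of those who were still observed. The before and after groups are not the same people, and the correlation between visits is not used to correct for who left.

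If patients with worse CAT scores are lost more heavily from one arm, that arm's 9-month mean drifts toward better scores with no treatment effect. A false benefit or a masked one could follow, on outcomes that the SAP tests at the 5% level.

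**Working it through.** **No figure of the plan to reproduce.** The documents give 29 per arm and the CAT range of 0 to 40, but no SD, between-visit correlation or attrition rate. Everything below that depends on these is an assumption.

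**Step 1: what independence GEE estimates.** With arm-by-visit terms the month-9 coefficient is

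(observed 9-month mean, intervention - baseline mean of all, intervention) - (the same for control).

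In simulated trials of 29 per arm, the fitted GEE coefficient matched this difference of cell means to rounding error (below 1e-14).

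**Step 2: its bias.** Let s be the completers' mean baseline score minus the all-patient mean, in SD units, and rho the baseline-to-month-9 correlation. If dropout depends on baseline score and there is no true effect,

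bias = SD x rho x (s_intervention - s_control).

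This is zero when the two shifts are equal. That covers random dropout at any pair of rates (both shifts 0) and the same rate with the same dependence in both arms.

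**Step 3: an illustration.** Assumptions: SD 8, rho 0.6, dropout 25% intervention and 10% control, logistic dependence on baseline CAT with log-odds 1 per SD (odds x 2.7). Integrating the logistic dropout curve over a standard normal baseline gives s = -0.213 at 25% dropout and -0.091 at 10%.

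- Dependence in the intervention arm only: 8 x 0.6 x (-0.213 - 0) = -1.02 points.
- Same slope in both arms: 8 x 0.6 x (-0.213 + 0.091) = -0.59 points.
- Slope halved in both arms (s = -0.120 and -0.049): 8 x 0.6 x (-0.120 + 0.049) = -0.34 points.
- Random dropout, 25% versus 10%: 0.

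**Step 4: effect on the test.** Simulated trials of 29 per arm (20,000 per row), independence GEE with the sandwich standard error and a two-sided 5% Wald test:

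| Dropout | Mean estimate | Type I error |
|---|---|---|
| None | 0 | 5.7% |
| 25% / 10%, random | 0 | 6.1% |
| 25% / 10%, same slope | -0.60 | 6.7% |
| 25% / 10%, intervention only | -1.02 | 8.5% |

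A repeat with 40,000 trials per row agreed to within simulation error. The fair comparator is the 6.1% under random dropout, because the small-sample sandwich test already exceeds 5% with no bias. The excess is 8.5 - 6.1 = 2.4 percentage points in the one-arm case and 6.7 - 6.1 = 0.6 with equal slopes. With a standard error of about 2.15 points, the largest bias here is 1.02 / 2.15 = 0.47 standard errors.

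**Step 5: sensitivity to the assumptions.** In large samples, with rho from 0.5 to 0.8 and 30% versus 10% dropout, the bias was -0.65 to -1.03 (same slope) and -1.01 to -1.61 (one arm only). With equal 20% dropout and opposite dependence it was -1.40 to -2.22, so equal rates are no safeguard.

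**Step 6: alternatives on the same data.** Likelihood with the correct correlation gave 0.0 in every one of these cases. In 400 trials of 29 per arm (rho 0.7, 30% versus 10%), exchangeable GEE averaged -0.02 where independence gave -0.95 (same slope), and -0.14 where independence gave -1.60 (one arm only). Likelihood cost no precision: under random dropout at 25% versus 10% with rho 0.6, its standard error was 2.08 against 2.15. Restricting to completers' change scores is not a remedy. Its bias is -(1 - rho) x SD x (s_intervention - s_control), which in the one-arm case is -0.4 x 8 x (-0.213) = +0.68, of opposite sign.

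**The case against.** The harm needs three links that the documents do not supply: that the default correlation was kept, that dropout is related to scores, and that this selection differs by arm. That stands, and it makes this a risk left open and not a bias shown.

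A reader might infer that unequal dropout is itself enough, or that any dependence of dropout on a patient's own scores is enough. Step 2 shows that neither is: the selection has to differ between arms.

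A reader might also infer that the protocol forecasts burden-driven loss from the intervention arm, because section 3(i), item 4 mentions "excessive burden created by the time required to participate in the study". That is safety-monitoring text about events that may lead to withdrawal. It is not specific to an arm and gives no rate. The intervention is heavier on paper (exercise five days a week under Step 6, against three control visits under item f), but exercise and the pharmacist meeting are optional and contacts can be tailored. Leaving the programme is also not the same as missing the outcome: dropout is tied to missed interviews after up to three reschedulings, interviews may be done by phone, and the payments in section 8 do not differ by arm.

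Nor do the documents show that intention-to-treat is breached. Independence GEE still uses every patient with data, but it needs a stronger assumption about who is missing.

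The last objection is that this is a feasibility trial, not powered for outcomes. That limits the consequence. It does not remove it, because the SAP still applies a 5% significance rule to all outcomes, and low power excuses imprecision but not an avoidable bias.

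**Conclusion.** The point holds as a conditional one. Run as written, with arm-by-visit terms and the software default, the 9-month difference-in-differences compares all patients at baseline with only those observed at 9 months, and nothing in the protocol repairs this. It would be biased by score-related dropout that selects differently in the two arms. Under the stated illustration the bias is about -0.6 to -1.0 CAT points, at most about half a standard error, with type I error about 7% to 8% against about 6% without the bias. Milder dependence gives less and opposite dependence gives more. The SD, correlation, dropout rates and slopes are all assumptions. The cell-mean identity and the conditions for zero bias hold whatever values are used. It is worth changing because a better method costs almost nothing, not because the result is known to be wrong.

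**What to change.** For continuous outcomes, replace the GENMOD analysis by a likelihood repeated-measures model: arm, visit and arm-by-visit, unstructured covariance over the three visits, REML, and a small-sample degrees-of-freedom correction such as Kenward-Roger. Use every randomised patient's available visits, and name the month-9 arm contrast as the primary result.

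If GENMOD is kept, specify an unstructured or exchangeable working correlation. State that this removes the bias only when the correlation is adequately specified and dropout depends on observed scores. State also how inhaler technique is scored. If it is not continuous, the linear model above does not carry over, and multiple imputation ahead of GENMOD is one option.

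Report 9-month completion by arm, with completers' and non-completers' baseline scores, so that a reader can judge whether selection differed. Optionally, add one sensitivity analysis for dropout that depends on unseen scores, which none of these models corrects.

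The cost is SAP wording, a few lines of SAS and a covariance assumption, with no new data. The SAP is written in the past tense, so if the analysis has already been run, rerun it and report the working correlation that was used.
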